1 STUDY SYNOPSIS

Study title

Lean Efficacy Phase IIa Proof of concept trial (LEAAP). A multi-centre, double-blind, placebo-controlled, randomised study in overweight and obese patients during twenty-six weeks, investigating the effect of EMP16-02 on body weight, safety and clinical biomarkers

Study code	EudraCT No
EP-002	2019-004545-32
Planned study period	Phase of development
Main part (Visits 1 to 6): Q2 2020 to Q2 2021 Follow-up part (Visit 7): Q2 2021 to Q3 2021	Phase IIa

Coordinating Investigator

[name] PhD CTC Clinical Trial Consultants AB [name] [contact]

E-mail: [contact]

Study design

This is an exploratory, randomised, double-blind, placebo-controlled study in overweight and obese patients in which the effect of two doses of EMP16-02 on body weight loss will be tested versus placebo. The main part of the study will be conducted during 26 weeks at two study centres in Sweden. Consenting subjects will continue in a 6 month follow-up part.

Objectives

Primary objective:

• To evaluate the effect of the study drug EMP16-02 (120 mg orlistat [O]/40 mg acarbose [A]) on relative body weight loss after a 26-week period of oral treatment as compared to placebo.

Secondary objectives:

- To assess the effect of two different doses of EMP16-02 (120 mg O/40 mg A and 150 mg O/50 mg A) on relative and absolute body weight loss during a 26-week period of oral treatment as compared to placebo.
- To assess the effect of two different doses of EMP16-02 (120 mg O/40 mg A and 150 mg O/50 mg A) on other anthropometric characteristics during a 26-week period of oral treatment as compared to placebo.
- To assess the effect of two different doses of EMP16-02 (120 mg O/40 mg A and 150 mg O/50 mg A) on satiety and meal pattern during a 26-week period of oral treatment as compared to placebo.
- To assess the effect of two different doses of EMP16-02 (120 mg O/40 mg A and 150 mg O/50 mg A) on fasting insulin, glucose metabolism markers, lipid metabolism markers and inflammation markers during a 26-week period of oral treatment as compared to placebo.

CONFIDENTIAL 3 (92)

- To assess the effect of two different doses of EMP16-02 (120 mg O/40 mg A and 150 mg O/50 mg A) on blood pressure during a 26-week period of oral treatment as compared to placebo.
- To assess the effect of two different doses of EMP16-02 (120 mg O/40 mg A and 150 mg O/50 mg A) on quality of life during a 26-week period of oral treatment as compared to placebo.
- To assess the relationship between drop-out(s) and tolerability for two different doses of EMP16-02 (120 mg O/40 mg A and 150 mg O/50 mg A) during a 26-week period of oral treatment as compared to placebo.
- To assess the safety and gastrointestinal (GI) tolerability of two different doses of EMP16-02 (120 mg O/40 mg A and 150 mg O/50 mg A) during a 26-week period of oral treatment as compared to placebo.

Exploratory objectives:

- To assess the effect of two different doses of EMP16-02 (120 mg O/40 mg A and 150 mg O/50 mg A) on fasting plasma/serum levels of apolipoprotein A1 (ApoA1) and apolipoprotein B (ApoB) during a 26-week period of oral treatment as compared to placebo.
- To assess the pre-dose plasma level of orlistat and acarbose at steady state.
- To evaluate the effect of two different doses of EMP16-02 (120 mg O/40 mg A and 150 mg O/50 mg A) on relative and absolute body weight loss 6 months after completion of a 26-week period of oral treatment as compared to placebo.
- To evaluate the effect of two different doses of EMP16-02 (120 mg O/40 mg A and 150 mg O/50 mg A) on HbA1c concentration 6 months after completion of a 26-week period of oral treatment as compared to placebo.
- To evaluate the effect of two different doses of EMP16-02 (120 mg O/40 mg A and 150 mg O/50 mg A) on blood pressure 6 months after completion of a 26-week period of oral treatment as compared to placebo.

Endpoints

Primary endpoint:

• Relative (%) change from baseline in body weight after 26 weeks of treatment with EMP16-02 (120 mg O/40 mg A) as compared to placebo.

Secondary endpoints:

- Absolute change from baseline in body weight after 14 and 26 weeks of treatment with EMP16-02 (120 mg O/40 mg A) as compared to placebo.
- Relative (%) and absolute change from baseline in body weight after 14 and 26 weeks of treatment with EMP16-02 (150 mg O/50 mg A) as compared to placebo.
- Proportion of patients with ≥5% and ≥10% decrease in body weight compared to baseline after 14 and 26 weeks of treatment with EMP16-02 (120 mg O/40 mg A and 150 mg O/50 mg A) as compared to placebo.
- Relative (%) and absolute change from baseline in body mass index (BMI) after 14 and 26 weeks of treatment with EMP16-02 (120 mg O/40 mg A and 150 mg O/50 mg A) as compared to placebo.
- Absolute change from baseline in waist circumference after 14 and 26 weeks of treatment with EMP16-02 (120 mg O/40 mg A and 150 mg O/50 mg A) as compared to placebo.
- Absolute change from baseline in sagittal diameter after 14 and 26 weeks of treatment with EMP16-02 (120 mg O/40 mg A and 150 mg O/50 mg A) as compared to placebo.

CONFIDENTIAL 4 (92)

- Relative (%) and absolute change from baseline in percentage body fat after 14 and 26 weeks of treatment with EMP16-02 (120 mg O/40 mg A and 150 mg O/50 mg A) as compared to placebo.
- Satiety and craving after 14 and 26 weeks of treatment with EMP16-02 (120 mg O/40 mg A and 150 mg O/50 mg A) as compared to placebo, corrected for satiety and craving after standardised breakfast at baseline.
- Relative (%) and absolute change from baseline in fasting haemoglobin A1c (HbA1c), glucose, insulin, total cholesterol, high-density lipoprotein (HDL), low-density lipoprotein (LDL), triglycerides, liver enzymes, albumin and high-sensitivity C-reactive protein (hs-CRP) after 7, 14 and 26 weeks of treatment with EMP16-02 (120 mg O/40 mg A and 150 mg O/50 mg A) as compared to placebo.
- Change from baseline in the proportion of diabetic (fasting glucose ≥ 7.0 mmol/L) and prediabetic patients (fasting glucose ≥ 6.1 mmol/L and < 7.0 mmol/L) after 14 and 26 weeks of treatment with EMP16-02 (120 mg O/40 mg A and 150 mg O/50 mg A) as compared to placebo.
- Relative (%) and absolute change from baseline in blood pressure after 14 and 26 weeks of treatment with EMP16-02 (120 mg O/40 mg A and 150 mg O/50 mg A) as compared to placebo.
- Change from baseline in quality of life after 26 weeks of treatment with EMP16-02 (120 mg O/40 mg A and 150 mg O/50 mg A) as compared to placebo.
- Dropout rate (overall and GI-related) following treatment with EMP16-02 (120 mg O/40 mg A and 150 mg O/50 mg A) as compared to placebo.
- Frequency and severity of adverse events (AEs) during 26 weeks of treatment with EMP16-02 (120 mg O/40 mg A and 150 mg O/50 mg A) as compared to placebo.
- Clinically significant relative (%) and absolute changes from baseline in safety laboratory parameters and ECG after 26 weeks of treatment, and in vital signs after 7, 14 and 26 weeks of treatment with EMP16-02 (120 mg O/40 mg A and 150 mg O/50 mg A) as compared to placebo.
- GI tolerability after 2, 4, 6, 8, 14 and 26 weeks of treatment with EMP16-02 (120 mg O/40 mg A and 150 mg O/50 mg A) as compared to placebo.
- Compliance after 7, 14 and 26 weeks of treatment with EMP16-02 (120 mg O/40 mg A and 150 mg O/50 mg A) as compared to placebo.

Exploratory endpoints:

- The absolute difference in fasting plasma/serum levels of ApoA1 and ApoB from baseline after 7, 14 and 26 weeks of treatment with EMP16-02 (120 mg O/40 mg A and 150 mg O/50 mg A) as compared to placebo.
- Pre-dose plasma concentrations of orlistat and acarbose after 26 weeks of treatment with EMP16-02 (120 mg O/40 mg A and 150 mg O/50 mg A).
- Relative (%) and absolute change in body weight from baseline, and from end of treatment at 26 weeks, to 6 months after end of treatment with EMP16-02 (120 mg O/ 40 mg A and 150 mg O/50 mg A) as compared to placebo.
- Relative (%) and absolute change in HbA1c from baseline, and from end of treatment at 26 weeks, to 6 months after end of treatment with EMP16-02 (120 mg O/ 40 mg A and 150 mg O/50 mg A) as compared to placebo.
- Relative (%) and absolute change in blood pressure from baseline, and from end of treatment at 26 weeks, to 6 months after end of treatment with EMP16-02 (120 mg O/ 40 mg A and 150 mg O/50 mg A) as compared to placebo.

CONFIDENTIAL 5 (92)

Clinical Study Protocol EP-002 Final version v3.0 12NOV2020

The exploratory analyses may not be reported in the clinical study report (CSR). 6-month data will be reported in an addendum to the CSR.

Number of patients planned

A total of 156 patients will be randomised in the study. Assuming a dropout rate of 20%, a total of 52 patients will be randomised to each treatment arm to achieve at least 41 evaluable patients per arm.

An evaluable patient in the main part is defined as a patient who has completed 26 weeks of treatment with investigational medicinal product (IMP). An evaluable patient in the follow-up part is defined as a patient who has completed 26 weeks of treatment with IMP and the 6 months follow-up visit.

Diagnosis and main eligibility criteria

- Male and female patients with overweight or obesity, defined as BMI \geq 30, or \geq 28 kg/m² in the presence of other risk factors (*e.g.*, hypertension, glucose dysregulation such as impaired glucose tolerance and type 2 diabetes mellitus (T2DM), and/or dyslipidaemia).
- Aged ≥ 18 and ≤ 75 years.
- Willing and able to give written informed consent for participation in the study.
- Body weight stable (<5% reported change during the three months preceding screening and randomisation).

Methodology

This is an exploratory randomised, double-blind, placebo-controlled study in which EMP16-02 or placebo will be taken orally three times daily (TID) together with the three main daily meals during 26 weeks. EMP16-02 will be given to obese patients with an initial BMI \geq 30 kg/m² or \geq 28 kg/m² in the presence of other risk factors (*e.g.*, hypertension, glucose dysregulation such as impaired glucose tolerance and T2DM, and/or dyslipidaemia). Prior to any study assessments, patients will be asked to provide signed informed consent to participate in the study. The main part of the study consists of 6 visits to the research clinic, including screening and a safety follow-up visit. Visit 7 will be a long-term follow-up visit scheduled 6 months after completion of the 26-weeks treatment. All patients completing the treatment period will be asked to participate in the long-term follow-up and a separate consent will be collected. There will be no overnight stays at the clinic. Screening (Visit 1) will take place from Day -28 to Day -1. An electronic diary will be used to provide the patients with questionnaires to be filled in during or shortly before/after the visits. At two extra occasions between Visit 4 and 5, the electronic diary will be used for collecting information on IMP compliance, AEs and use of concomitant medication.

Eligible and consenting patients will arrive at the research clinic in the morning of the first dosing day (Day 1, Visit 2) after at least 8 hours overnight fasting. A re-check of eligibility including a brief physical examination, vital signs and assessment of body weight will be conducted.

The patients will be randomised to either of two doses of EMP16-02 or placebo:

- 1. EMP16-02 120 mg O/40 mg A
- 2. EMP16-02 150 mg O/50 mg A
- 3. Placebo (identical capsules)

Blood sampling (fasting), and anthropometric measurements will be performed. Patients will receive electronic diary instructions and will be asked to fill in a satiety and craving questionnaire before breakfast (at the clinic), and then once every hour for 4 hours until before lunch (at home). A standardised breakfast will be served at the clinic. Halfway through breakfast at Visit 2, all patients will receive a placebo capsule independent of the treatment arm to which the patients have been randomised, to provide patients with the opportunity to train on self-administering the IMP under supervision of clinic staff. The patients will also receive instructions for filling in more questionnaires

CONFIDENTIAL 6 (92)

Clinical Study Protocol EP-002 Final version v3.0 12NOV2020

regarding health and quality of life, meal pattern, activity and sleep, and gastrointestinal symptoms (gastrointestinal rating scale [GSRS]).

The patients will be instructed to take EMP16-02 or placebo halfway through each meal, together with approximately 100-200 mL water (or other drink) on all subsequent treatment days. Once IMP has been handed out, the patients are free to leave the clinic. The first randomised IMP dose will be taken during lunch (or the next meal) at home.

Patients randomised to EMP16-02 will start with a run-in period of 6 weeks during which the dose is sequentially increased. From week 7, all patients will have reached their final intended dose and a 20-week treatment and observation period will start. The run-in phase will start at a dose of 60 mg O and 20 mg A TID, which will sequentially be increased with 30 mg O/10 mg A every two weeks until the target doses of 120 mg O/40 mg A TID (for the lower dose group) and 150 mg O/50 mg A TID (for the higher dose group) are reached. The dosing regimen is as follows:

Target dose	Week 1 and 2	Week 3 and 4	Week 5 and 6	Week 7 to 26
EMP16-02 120 mg O/40 mg A	60 mg O/20 mg A	90 mg O/30 mg A	120 mg O/40 mg A	120 mg O/40 mg A
EMP16-02 150 mg O/50 mg A	60 mg O/20 mg A	90 mg O/30 mg A	120 mg O/40 mg A	150 mg O/50 mg A

Placebo treatment consists of matching oral capsules. Placebo and EMP16-02 capsules need to be taken TID together with three daily meals.

Patients will come to the clinic at Visit 3 (week 7), Visit 4 (week 14) and Visit 5 (week 26) for safety assessments and assessments of weight and anthropometric measurements. Patients will arrive in the morning after at least 8 hours overnight fasting. All visits will start with a brief physical examination followed by blood sampling (fasting) and assessment of body weight and body composition. A standardised breakfast will be served during which the patient will take the IMP. All or a selection of the questionnaires, including the satiety and craving questionnaire, will be filled in in a similar way as during Visit 2.

After 18 and 22 weeks of treatment (Day 123 ± 3 days and Day 151 ± 3 days, respectively), patients will be asked to answer questions about IMP compliance, occurrence of AEs and use of concomitant medication using an electronic diary.

New IMP will be handed out to the patients at Visit 2, 3 and 4.

At Visit 5 (week 26), the patients will take the last dose during breakfast at the clinic. Visit 6 is a safety follow up visit. Visit 7 is a 6 month follow-up visit for consenting patients who has completed the 26-week treatment period with active EMP16-02 treatment (120 mg O/40 mg A and 150 mg O/50 mg A) or placebo.

Investigational Medicinal Product (IMP), dosage and mode of administration

[figure not shown]
EMP16-02 is an oral, modified-release (MR) fixed dose combination (FDC) of orlistat and acarbose formulated in capsules, available in two strengths:

- EMP16-02-90/30, containing 90 mg O/30 mg A
- EMP16-02-60/20, containing 60 mg O/20 mg A

Two different doses of EMP16-02 will be used in the study (after a 6-week run-in period):

- 120 mg O/40 mg A (2 capsules EMP16-02-60/20)
- 150 mg O/50 mg A (1 capsule EMP16-02-90/30 and 1 capsule EMP16-02-60/20)

CONFIDENTIAL 7 (92)

Placebo is a matching, oral capsule. EMP16-02 and placebo should be taken three times daily (TID) together with three main daily meals.

Duration of treatment

Each patient will receive three daily doses of EMP16-02 or matching placebo during 26 weeks. The IMP will be taken together with the main daily meals.

Duration of each patient's involvement in the study

Each patient in the main part of the study will participate in the study for approximately 32 weeks including a screening period of up to 4 weeks, 26 weeks of treatment and a safety follow-up visit 2 weeks after the last treatment. Patients giving their consent to participate in a 6 month follow-up evaluation will participate in the study for 58 weeks including a screening period of up to 4 weeks, 26 weeks of treatment, a safety follow-up visit 2 weeks after the last treatment and a follow-up visit 26 weeks after the last treatment.

Efficacy assessments

Weight, other anthropometric measurements (BMI, waist circumference, sagittal diameter, bio-impedance), blood sampling for fasting lipid metabolism, glucose metabolism and inflammations markers, blood pressure, questionnaires (meal pattern, GSRS, satiety and craving, activity and sleep and health and quality of life [RAND-36]), drop-out rate (assessed both in terms of safety and efficacy).

Safety assessments

AE recording, vital signs (blood pressure assessed both in terms of safety and efficacy), ECG, fasting safety laboratory blood sampling, physical examination, GSRS (assessed both in terms of safety and efficacy).

Exploratory assessments

Fasting blood sampling for ApoA1 and ApoB, pre-dose blood sampling for orlistat and acarbose plasma concentrations at steady state. Weight, HbA1c and blood pressure 6 months after end of treatment.

Statistical methods

The primary endpoint, relative (%) change from baseline in body weight after 26 weeks of treatment with EMP16-02 (120 mg O/40 mg A) as compared to placebo, will be analysed using analysis of variance with treatment as independent variable.

The absolute change from baseline in body weight after 14 and 26 weeks of treatment with EMP16-02 (120 mg O/40 mg A) as compared to placebo will be analysed using analysis of covariance with treatment and body weight at baseline as covariates.

The relative (%) change from baseline in body weight after 14 and 26 weeks of treatment with EMP16-02 (150 mg O/50 mg A) as compared to placebo will be analysed using analysis of variance with treatment as independent variable. The relative and absolute change in body weight from baseline, and from end of treatment at 26 weeks, to 6 months after completion of the 26-week treatment period will be analysed by corresponding means.

The proportion of patients with \geq 5% and \geq 10% decrease in body weight compared to baseline after 14 and 26 weeks of treatment with EMP16-02 (120 mg O/40 mg A and 150 mg O/50 mg A) as compared to placebo will be analysed using Chi-square test without continuity correction.

Other anthropometric parameters, glucose metabolism markers, lipid metabolism markers, inflammation markers and blood pressure will also be analysed using analysis of variance. For

CONFIDENTIAL 8 (92)

Clinical Study Protocol EP-002 Final version v3.0 12NOV2020

relative changes from baseline, treatment will be used as independent variable. For absolute changes from baseline, treatment and body weight will be used as covariates.

The proportions of diabetic patients, prediabetic patients and non-diabetic patients after 14 and 26 weeks of treatment with EMP16-02 (120 mg O/40 mg A and 150 mg O/50 mg A) will be presented using shift tables. The change from baseline in the proportion of diabetic and prediabetic patients after 14 and 26 weeks of treatment with EMP16-02 as compared to placebo will be analysed using Chi-square test without continuity correction.

Meal pattern, satiety and craving and health and quality of life (RAND-36) questionnaires will be analysed using the Wilcoxon Rank Sum test. The GSRS questionnaire will be analysed using analysis of covariance while the activity and sleep questionnaire will be analysed using a Chi-square test. The drop-out rate (overall and GI-related) following treatment with EMP16-02 (120 mg O/40 mg A and 150 mg O/50 mg A) as compared to placebo will be analysed using Chi-square test without continuity correction.

Continuous data will be presented in terms of evaluable and missing observations, arithmetic mean, standard deviation (SD), median, minimum and maximum value.

Categorical data will be presented as counts and percentages. When applicable, summary data will be presented by treatment, and by assessment time. Individual patient data will be listed by treatment, patient number, and, where applicable, by assessment time.

All descriptive summaries and statistical analyses will be performed using SAS Version 9.4 or later (SAS Institute, Inc., Cary, NC).

Baseline is defined as the visit with last data collection point prior to the first administration of IMP.

All hypothesis testing will use a significance level of 5%.

Comparisons will be made pairwise and analysed at each visit if not stated otherwise.

Study reporting

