17.6.5 Questionnaires

17.6.5.1 Meal pattern questionnaire

For each treatment group, the absolute and percent change from baseline in total score of the Meal pattern questionnaire will be calculated and analysed using the Wilcoxon Rank Sum test at each visit. The absolute change for each question will be compared between the treatment groups by using the Wilcoxon Rank Sum test.

CONFIDENTIAL 84 (92)

Clinical Study Protocol EP-002 Final version v3.0 12NOV2020

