17.6.5.2 Gastrointestinal tolerability questionnaire

For each treatment group, the absolute and percent change from baseline in total score of the GSRS be calculated and analysed using analysis of covariance with at least treatment, weight at baseline as covariates. More covariates will be addressed in the SAP.

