17.6.5.3 Satiety and craving

Satiety and craving as total score after 14 and 26 weeks of treatment with EMP16-02 (120 mg O/40 mg A and 150 mg O/50 mg A) as compared to placebo, corrected for hunger and craving after standardised breakfast at baseline will be analysed using the Wilcoxon Rank Sum test. Each individual question may be analysed, if so, will this be described in the SAP.

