17.6.5.5 Health and quality of life (RAND-36)

The change from baseline in quality of life after 26 weeks of treatment with EMP16-02 (120 mg O/40 mg A and 150 mg O/50 mg A) as compared to placebo will be analysed using the Wilcoxon Rank Sum test.

17.6.6 **Drop-out rate**

The drop-out rate (overall and GI-related) following treatment with EMP16-02 (120 mg O/40 mg A and 150 mg O/50 mg A) as compared to placebo will be analysed using Chi-square test without continuity correction.

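### Meal pattern and RAND-36 are tested by an unadjusted Wilcoxon test on change from baseline: valid, but it loses power against a rank covariance analysis when baseline and follow-up correlate weakly or moderately

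*Protocol*

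**What the plan says.** The synopsis (Statistical methods) names one test for three questionnaires: "Meal pattern, satiety and craving and health and quality of life (RAND-36) questionnaires will be analysed using the Wilcoxon Rank Sum test". Section 17 then sets what is tested for each.

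- **Meal pattern (17.6.5.1):** "absolute and percent change from baseline in total score of the Meal pattern questionnaire will be calculated and analysed using the Wilcoxon Rank Sum test". For the single items, "The absolute change for each question will be compared between the treatment groups by using the Wilcoxon Rank Sum test".
- **RAND-36 (17.6.5.5):** the variable is "The change from baseline in quality of life after 26 weeks of treatment with EMP16-02" compared with placebo, again by Wilcoxon.
- **Satiety and craving (17.6.5.3):** the total score, "corrected for hunger and craving after standardised breakfast at baseline will be analysed using the Wilcoxon Rank Sum test". How the correction is made is not stated.

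No covariate is named for any of these tests. The fourth scored questionnaire, the GSRS (17.6.5.2), is "analysed using analysis of covariance with at least treatment, weight at baseline as covariates. More covariates will be addressed in the SAP".

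Table 11.5-2 schedules all of these questionnaires at Visit 2, so each scale has its own baseline value. The protocol states no power, effect size, SD or correlation for any questionnaire.

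**The concern.** A rank-sum test takes no covariate. When it is applied to a change score, the baseline enters by subtraction, which fixes its slope at 1. The best slope for two scores with equal variance is their correlation r, which is below 1 for any imperfectly reproducible scale. Subtraction therefore over-corrects and carries part of the baseline noise into the outcome. Below r = 0.5, a change score is less precise than the follow-up score with baseline ignored. The percent change in the meal pattern total is also a fixed function of baseline with nothing estimated.

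At stake is the chance of detecting a real effect under the secondary objectives on meal pattern and quality of life, with about 41 evaluable patients per arm and the needed baseline already collected.

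**Working it through.** **Inputs from the protocol.** 41 evaluable patients per arm, two-sided 5% level (17.2). Meal pattern has five items scored 0-3 (11.5.4.1), so its total runs from 0 to 5 × 3 = 15. Comparisons are pairwise at each visit (17.1).

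**Assumptions, not in the protocol.** Baseline to follow-up correlation r, shown from 0.3 to 0.9. True effect 0.5 SD, with 0.6 SD as a second case. Equal SD at both visits.

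**Step 1: the plan's own figure.** For body weight, a difference of 5 with SD 8 gives n = 2 × (1.960 + 0.842)² × 8² / 5² = 40.2, hence 41 per arm. With 20% dropout, 41 / 0.8 = 51.25, hence 52 per arm and 3 × 52 = 156. The stated sample size reproduces. It says nothing about the questionnaires; it only supplies the 41.

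**Step 2: precision.** Relative to the variance of the follow-up score alone, a change score has variance 2(1 − r) and a covariance analysis 1 − r². Their ratio is (1 − r²) / [2(1 − r)] = (1 + r) / 2. With a normal approximation, power = Φ(0.5 / √(2v/41) − 1.96), where v is the relative variance.

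| r | v, change | v, covariance | ratio | power, change | power, covariance |
|---|---|---|---|---|---|
| 0.3 | 1.40 | 0.91 | 0.65 | 48% | 66% |
| 0.5 | 1.00 | 0.75 | 0.75 | 62% | 74% |
| 0.7 | 0.60 | 0.51 | 0.85 | 83% | 89% |
| 0.8 | 0.40 | 0.36 | 0.90 | 95% | 97% |
| 0.9 | 0.20 | 0.19 | 0.95 | 99.9% | 99.9% |

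**Step 3: the rank tests themselves.** Simulation with 41 per arm, 4,000 replicates per setting, and normal scores rounded to 0-15 (mean 8, SD 3). Wilcoxon on change is compared with Quade's rank analysis of covariance, at an effect of 0.5 SD.

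| r | Wilcoxon on change | Quade | loss, points |
|---|---|---|---|
| 0.3 | 45% | 62% | 17 |
| 0.5 | 57% | 69% | 12 |
| 0.7 | 78% | 83% | 5 |
| 0.8 | 91% | 92% | 1 |
| 0.9 | no gain | no gain | 0 |

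At 0.6 SD and r = 0.7 the powers are about 91% and 94%, a loss of about 3 points. With smaller effects, set so that a covariance analysis has 80% nominal power, the order reverses at r = 0.9: Wilcoxon on change is ahead by about 3 points.

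**Step 4: validity.** With no true effect, both tests reject close to 5% of the time.

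**The case against.** The strongest reply is that nothing here is wrong. Both tests hold their level, the RAND-36 endpoint is itself defined as a change from baseline, the study is exploratory, and only body weight is powered. The loss rests on a correlation that the documents do not give, and at 0.8 or above there is almost nothing to gain. All of this stands, and it sets the severity.

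Four stronger readings are tempting, and the documents do not support them.

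- **That the test ignores baseline.** It does not; subtraction uses it. What is missing is an estimated slope.
- **That chance baseline imbalance makes the test invalid.** Among simulated trials with no effect, about 17% had a baseline difference above 0.3 SD. In those, Wilcoxon on change rejected 14%, 10% and 8% of the time at r = 0.3, 0.5 and 0.7, against 4-5% for Quade. Over all randomisations, however, the error rate is 5%, so this is a reason to prefer adjustment and not a failure of the test.
- **That satiety and craving is also tested on subtracted scores.** Section 17.6.5.3 speaks only of a correction. Removing a regression on baseline and ranking the residuals would also satisfy it.
- **That the GSRS sets a precedent for adjusting a scale for its own baseline.** The only baseline covariate named in 17.6.5.2 is body weight, with others left to the SAP.

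It is also fair to say that the simulated 0-15 score represents the meal pattern total. RAND-36 has 36 questions, and nothing in the protocol shows that its correlation is low.

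**Conclusion.** The point holds as a conditional loss of efficiency for meal pattern and RAND-36. The protocol fixes an unadjusted rank-sum test on change for both, and defers nothing in those two subsections to the SAP. At an effect of 0.5 SD the loss runs from about 17 points of power at r = 0.3 to none at 0.9. No single figure can be quoted without its r. The size applies most directly to the meal pattern total and is only indicative for RAND-36.

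For satiety and craving the finding is only that the correction is undefined. Severity is low: these are secondary analyses with no stated power, and neither the error rate nor the primary result is affected.

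**What to change.** In 17.6.5.1, 17.6.5.5 and the synopsis, name a rank analysis of covariance (Quade) as the main test. Rank the follow-up score, remove its regression on the rank of the same scale's Visit 2 score, and compare the residuals between arms. Keep the Wilcoxon test on change as a sensitivity analysis, which also preserves the link to the endpoint as worded.

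In 17.6.5.3, state that the correction for baseline is this same rank covariance adjustment.

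The cost is a few lines of wording and of SAS code, with no new data. The downside is slightly more analysis work, with little or no gain if the correlation proves to be 0.8 or higher.
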